# 10.4.4 Reporting

# 10.4.4.1 Actions Required by Investigators

Actions required by Investigators for reporting of adverse events are summarized in Table 1 and Table 2 below.

**Table 1. Non-serious Ocular Adverse Events** 

Non-serious ocular AEs	Non-device-related	Device-related
i Keduli ed Action	Recorded on Adverse Even no expedited report to Heal	t CRF only; th Canada, Sponsor, or IRB/IEC

Table 2. Serious Adverse Events

SAEs	Non-device-related	Device-related (SADE)
	-Recorded on SAE Report	-Recorded on SAE Report Form and
	Form and AE CRF.	AE CRF
Required Action	-Investigator submits expedited report to Sponsor and its representative within 48 hours.	-Investigator submits expedited report to Sponsor and its representative within 48 hours.
	-Report to IRB/IEC if required per IRB/IEC policy.	-Report to IRB/IEC within 10 days, or earlier if required per IRB/IEC policy.

	- Investigator must also submit SADE as a Mandatory Problem Report to HC within 72 hours of discovery.

# 10.4.4.2 SAE Reporting

The Investigator must report any serious adverse event (related or unrelated) to the Sponsor and its representative in an expedited manner if it meets the criteria for a SAE.

The Investigator must forward the SAE/SADE Report Form and any available supporting documents to the Sponsor or its designee within 48 hours of becoming aware of an event.

The contact for reporting SAEs is:

The contact for reporting SADEs is:

All device related serious adverse events (SADEs) must be reported to the reviewing IRB/IEC within no more than 10 working days following first awareness of the SADE or according to the established reporting timelines of the IRB/IEC, whichever is shorter. If required, the Investigator must also report non-device related serious adverse events (SAEs) to the reviewing IRB/IEC according to the established reporting procedures and timelines. When participating in multicenter clinical investigations, the Investigator also may receive off-site SAE reports. These are reports of SAEs which occurred at other clinical sites for the same trial, or in different trials, but with the same investigational device. The Investigator must forward such reports to IRB/IEC according to the established reporting procedures within 10 days or earlier if required by IRB/IEC. When participating in multicenter clinical investigations,

Principal Investigators also may receive off-site SADE reports. These are reports of SADEs which occurred at other clinical sites for the same trial, or in different trials

# 10.4.4.3 Mandatory Problem Reporting

The qualified investigator is required to report any Mandatory Problems to Health Canada within 72 hours of discovery. Mandatory Problems are cases in which the incident:

• Is related to a failure of the device or a deterioration in its effectiveness, or any inadequacy in its labelling or in its directions for use.

#### and

• Has led to the death or a serious deterioration in the state of health of a patient, user or other person, or could do so were it to recur. A serious deterioration in health means a life-threatening disease, disorder or abnormal physical state, the permanent impairment of a body function or permanent damage to a body structure, or a condition that necessitates an unexpected medical or surgical intervention to prevent such a disease, disorder or abnormal physical state or permanent impairment or damage. The term "permanent" means irreversible impairment or damage to a body structure or function, and necessarily excludes minor impairment or damage. Medical intervention is not in itself a serious deterioration in health. The reason that motivated the medical intervention should be used to assess the reportability of an incident.

For this protocol, all SADEs will be Mandatory Problems.

The contacts for Mandatory Problem Reporting for Health Canada are as follows:

Email: [contact]

Or

[contact]

Any reports which are reported to Health Canada as a Mandatory Problem, must also be submitted to the Sponsor per applicable timelines.

# 10.4.4.3.1 Mandatory Problem Reporting by Sponsor

A Preliminary Report will be sent to Health Canada, IRB/IEC, and investigators:

• Within 10 days after Sponsor becomes aware of a Mandatory Problem that has led to the death or a serious deterioration in the state of health of a patient, user or other person, or

• Within 30 days after Sponsor becomes aware of a Mandatory Problem, if the Mandatory Problem has not led to the death or a serious deterioration in the state of health of a patient, user or other person, but could do so were it to recur.

A Final Report will be submitted to Health Canada, IRB/IEC, and investigators upon final assessment of the Preliminary Report by the Sponsor.

### **10.4.4.4** Reporting Device Deficiencies

A device deficiency is defined as an inadequacy of a medical device with respect to its identity, quality, durability, reliability, safety or performance. Device deficiencies include malfunctions, use errors, and inadequate labeling.

Investigators must evaluate, record, and report via applicable forms any complaints/deficiencies or malfunctions experienced with a Test or Control lens during this trial to the Sponsor and its representative promptly. The Sponsor shall review all device deficiencies, and, upon the Sponsor's request, Investigators must supply any additional information related to the safety reporting of a particular event. Test and Control lenses that are associated with a device deficiency are to be returned to the Sponsor or their representative without delay.

If the device deficiency is associated with or caused an SAE, then the device deficiency meets the criteria of a Mandatory Problem, then the Mandatory Problem Reporting procedure and timelines must be followed as per Section 10.4.4.3 in addition to device deficiency reporting procedures.

If no SAE/SADE was associated with or caused by the device deficiency, then the following assessment must also be made for the deficiency:

• Deficiency might have led to an SAE/SADE if suitable action had not been taken or intervention had not been made or if the circumstance had been less fortunate

The contact for reporting device deficiencies is:

# 10.4.4.4.1 Reporting of Deficiencies for Marketed Products

Any deficiency related to ancillary marketed products used in this study should be reported by the Investigators to the Sponsor or manufacturer according to the marketed product directions for use, and to other parties in accordance with the country and regional requirements.

# 10.4.5 Adverse Events at Subject Exit

Ongoing AEs will be followed until resolution, no further change in the condition is expected (i.e., event stabilized), or as dictated by standard of care. Documentation in the CRF of this follow-up is not required although subject care should continue as appropriate.

Ongoing SAEs and SADEs will be followed by the Sponsor and its representative(s) and the Investigator until the outcome is determined or until no further change in the condition is expected.

# 10.4.6 Pregnancy

During the study, all female subjects of childbearing potential should be instructed to contact the investigator immediately if they suspect they might be pregnant (e.g., missed or late menstrual period). Female subjects who become pregnant during the study will be followed until completion of pregnancy. Every effort will be made to obtain the health status of the mother and infant or fetus (in cases of miscarriage or therapeutic abortion) at term. Pregnancy itself is not considered an AE.

All confirmed pregnancies must be immediately reported to the medical monitor and CRO contact within 48 hours of the investigator's awareness of the pregnancy. All confirmed pregnancies must be reported via confirmed facsimile or email transmission and must be submitted on a Pregnancy Report form to the Sponsor or designee within 48 hours of the investigator's awareness of the pregnancy.

The contact for reporting pregnancies is:

#### 11 Statistics

# 11.1 Hypotheses

The purposes of this clinical investigation are to show that the Test lens, when implanted in the capsular bag, is safe and that, compared to an aspheric monofocal IOL, the lens provides improved intermediate and near visual acuity while maintaining comparable distance visual acuity.

The critical region for rejection of null hypotheses will be a p-value  $\leq 0.05$  unless otherwise specified. This applies to one-sided hypotheses as is customary for IOL trials.

#### 11.1.1 Safety Endpoints

# 11.1.1.1 First Primary Safety Endpoint

The goal of this endpoint is to estimate the proportion of eyes with at least one serious adverse event. There is no statistical hypothesis associated with the proportion of first implanted ITT eyes with at least one serious adverse event through Form 4 (Visit 4, Day 120 to Day 180 after second eye IOL implantation).

# 11.1.1.2 Second Primary Safety Endpoint

The goal of this endpoint is to estimate the proportion of eyes with at least one secondary surgical intervention due to the optical properties of the lens. The second primary safety endpoint is the rate of secondary surgical interventions due to the optical properties of the lens through Form 4 (Visit 4, Day 120 to Day 180 after second eye IOL implantation). There is no statistical hypothesis associated with this endpoint.

# 11.1.1.3 Third Primary Safety Endpoint

The goal of this endpoint is to determine whether the rate of any ISO grid AE is inferior to the historical control rate. For each ISO 11979-7:2018 Annex E SPE grid AE, the null and alternative hypotheses are as follows:

$$H_0: \pi \le \pi_0$$
  
 $H_1: \pi > \pi_0$ 

Where:

- $\pi$  = the proportion of Test (trifocal) eyes with the adverse event, and
- $\pi_0$  = the historical control proportion of eyes with the adverse event given in the ISO 11979-7 SPE grid

# 11.1.2 Performance Endpoints

#### 11.1.2.1 Primary Performance Endpoints

### 11.1.2.1.1 First Primary Performance Endpoint: UDVA

The goal of the first primary performance evaluation is to show that the Test lens is noninferior to the Control lens in uncorrected distance visual acuity. For the first primary performance endpoint, mean photopic monocular logMAR UDVA in first implanted eyes at Post-Operative Visit 4, the null  $(H_0)$  and alternative  $(H_1)$  hypotheses are as follows:

$$H_0$$
:  $\mu_T - \mu_C \ge 0.2$   
 $H_1$ :  $\mu_T - \mu_C < 0.2$ 

Where:

- $\mu_T$  = the mean logMAR UDVA of the Test (trifocal) group, and
- $\mu_C$  = the mean logMAR UDVA of the Control (monofocal) group

# 11.1.2.1.2 Second Primary Performance Endpoint: UNVA

The goal of the second primary performance evaluation is to show that the Test lens is superior to the Control lens in uncorrected near visual acuity. For the second primary performance endpoint, mean photopic monocular logMAR UNVA in first implanted eyes at Post-Operative Visit 4, the null and alternative hypotheses are as follows:

$$H_0: \mu_T = \mu_C$$
  
 $H_1: \mu_T \neq \mu_C$ 

Where:

- $\mu_T$  = the mean logMAR UNVA of the Test (trifocal) group, and
- $\mu_C$  = the mean logMAR UNVA of the Control (monofocal) group

# 11.1.2.1.3 Third Primary Performance Endpoint: UIVA

The goal of the third primary performance evaluation is to show that the Test lens is superior to the Control lens in uncorrected intermediate visual acuity. For the third primary performance endpoint, mean photopic monocular logMAR UIVA in first implanted eyes at Post-Operative Visit 4, the null and alternative hypotheses are as follows:

$$H_0: \mu_T = \mu_C$$
  
 $H_1: \mu_T \neq \mu_C$ 

Where:

 $\mu_T$  = the mean logMAR UIVA of the Test (trifocal) group, and  $\mu_C$  = the mean logMAR UIVA of the Control (monofocal) group

#### 11.1.2.2 Secondary Performance Endpoints

#### 11.1.2.2.1 Rotational Stability

The goal of this endpoint is to show that the rotational stability of the enVista® Trifocal IOL is acceptable. Trifocal IOL rotational stability will be determined from photographic evidence evaluated at an independent central reading center (*cf.* **Appendix B**, **Section 12.0**) and judged by criteria contained in ISO 11979-7:2018 Section 6.2.2.

#### 11.1.2.2.2 Change from Baseline in UNVA

The goal of the second secondary performance evaluation is to show that uncorrected near visual acuity after cataract removal and implantation of the Test lens is superior to the near acuity achieved by the same eye in its cataractous presurgical state with its natural refractive errors. For mean change from baseline in photopic monocular logMAR UNVA in first implanted eyes in the Test lens group at Post-Operative Visit 4, the null and alternative hypotheses are as follows:

$$H_0: \mu_d \ge 0$$

$$H_1$$
:  $\mu_d < 0$ 

Where:

•  $\mu_d$  = the mean change from baseline in photopic uncorrected near visual acuity (UNVA) for first implanted eyes in the Test lens group at 40 cm at Post-Operative Visit 4 (Day 120 to Day 180 after second eye implantation)

# 11.1.2.2.3 Change from Baseline in UIVA

The goal of the second secondary performance evaluation is to show that uncorrected intermediate visual acuity after cataract removal and implantation of the Test lens is superior to the intermediate acuity achieved by the same eye in its cataractous presurgical state with its natural refractive errors. For mean change from baseline in photopic uncorrected intermediate visual acuity (UIVA) for first implanted eyes in the Test lens group at 66 cm at Post-Operative Visit 4 (Day 120 to Day 180 after second eye implantation), the null and alternative hypotheses are as follows:

$$H_0: \mu_d \ge 0$$
  
 $H_1: \mu_d < 0$ 

Where:

 $\mu_d$  = the mean change from baseline in photopic uncorrected intermediate visual acuity (UIVA) for first implanted eyes in the Test lens group at 66 cm at Post-Operative Visit 4 (Day 120 to Day 180 after second eye implantation)

# 11.2 Sample Size Determination

# 11.2.1 Primary Performance Endpoint Sample Sizes

#### 11.2.1.1 UDVA

When the sample sizes in the Test and Control groups are 100 and 50 subjects, respectively, a two group one-sided 0.05 significance level t-test will have > 99% power to reject the null hypothesis that the test is inferior to the standard in favor of the alternative hypothesis that the treatment is non-inferior, assuming that the expected difference in means is 0, a non-inferiority margin is 0.2 and the common standard deviation is 0.15.

#### 11.2.1.2 UNVA

A two-group t-test with a 5% two-sided significance level will have > 99% power to detect a difference in means of 0.2, assuming that the common standard deviation is 0.15, when the sample sizes in the two groups are 100 and 50, respectively (a total sample size of 150).

# 11.2.1.3 UIVA

A two-group t-test with a 5% two-sided significance level will have > 99% power to detect a difference in means of 0.2, assuming that the common standard deviation is 0.15, when the sample sizes in the two groups are 100 and 50, respectively (a total sample size of 150).

#### 11.2.2 Sub-Studies

#### 11.2.2.1 Defocus Curves

At least ten (10) Test enVista trifocal IOL subjects and ten (10) Control enVista monofocal IOL subjects will be evaluated to obtain defocus curves as described in **Appendix B**, **Section 9.0**, in each of the following pupil size groups: small ( $\leq 3.0 \text{ mm}$ ), medium (> 3.0 mm and  $\leq 4.0 \text{ mm}$ ), and large (> 4.0 mm), as determined under photopic lighting conditions. The defocus curve sub-study subjects will be enrolled sequentially. If ten subjects are not available in any pupil size category for a treatment group, then the maximum number available will be used.

# 11.2.2.2 Contrast Sensitivity

At least approximately 50 bilaterally implanted Test trifocal IOL subjects and 25 bilaterally implanted Control monofocal IOL subjects will participate in the contrast sensitivity sub-study. Subjects who participate in the contrast sensitivity study will likely not participate in the defocus curve sub-study. Subjects who continue in the study with only one eligible eye also are likely not eligible for the contrast sensitivity sub-study. To allow for losses of up to 10%, at least approximately 56 Test trifocal IOL subjects and 28 Control monofocal IOL subjects will be enrolled in the sub-study.

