#### 11.2.3 Overall Sample Size and Adjustment for Dropouts

To allow for losses of up to 10%, approximately [100/(1-0.1)] = 112 Test group subjects and approximately [50/(1-0.1)] = 56 Control group subjects will be enrolled. The overall enrollment target will be approximately 168 subjects.

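### Are there too few Control subjects to fill both the defocus curve and the contrast sensitivity sub-studies?

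*Combined protocol and SAP*

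**What the plan says.** Three parts of the protocol bear on this.

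- **Defocus curves (Section 11.2.2.1).** "At least ten (10) Test enVista trifocal IOL subjects and ten (10) Control enVista monofocal IOL subjects will be evaluated", and this applies "in each of the following pupil size groups: small", medium and large. The section then provides for a shortage: "If ten subjects are not available in any pupil size category for a treatment group, then the maximum number available will be used".
- **Contrast sensitivity (Section 11.2.2.2).** "At least approximately 50 bilaterally implanted Test trifocal IOL subjects and 25 bilaterally implanted Control monofocal IOL subjects will participate". With an allowance for 10% loss, "at least approximately 56 Test trifocal IOL subjects and 28 Control monofocal IOL subjects will be enrolled in the sub-study". On the relation between the two sub-studies: "Subjects who participate in the contrast sensitivity study will likely not participate in the defocus curve sub-study".
- **Trial size (Section 11.2.3).** "approximately [50/(1-0.1)] = 56 Control group subjects will be enrolled". The Synopsis expects 100 Test and 50 Control subjects to complete.

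Appendix A schedules both tests at Visit 4 only, on a subset of subjects. Section 6.3.4 leaves both out of an early final visit. The data therefore come from subjects who reach Visit 4.

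**The concern.** Randomization is 2:1, but the defocus target is the same in both arms, so the smaller Control arm carries a proportionally heavier load. If the two sub-studies are read as separate groups, their Control sizes add up to more than the arm can supply, and the protocol does not remark on it. One of the two would then miss its stated minimum because of how subjects are divided, even with good retention and an even spread of pupil sizes.

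The sub-studies have some weight. Contrast sensitivity is a secondary safety variable, and Section 10.3 names this sub-study as a way of evaluating a known risk of multifocal lenses. The defocus curve is the supportive evidence on range of vision. A thin Control group would weaken the comparison in either.

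**Working it through.** **Inputs.** Defocus: 10 per pupil group, 3 groups (11.2.2.1). Contrast sensitivity: 25 Control and 50 Test participating, 28 and 56 enrolled (11.2.2.2). Trial: 56 Control and 112 Test enrolled (11.2.3), 50 and 100 expected to complete (Synopsis). Loss: up to 10%.

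**Step 1: the plan's own figures.** Enrolled = completers / (1 − 0.1), rounded up.

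- 25 / 0.9 = 27.8, so 28
- 50 / 0.9 = 55.6, so 56
- 100 / 0.9 = 111.1, so 112

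All three match the protocol.

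**Step 2: demand if no subject does both tests.** Defocus demand is 3 × 10 = 30 per arm. On the enrolled basis it becomes 30 / 0.9 = 33.3, so 34.

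| Basis | Control needed | Control available | Test needed | Test available |
|---|---|---|---|---|
| Completers | 30 + 25 = 55 | 50 | 30 + 50 = 80 | 100 |
| Enrolled | 34 + 28 = 62 | 56 | 34 + 56 = 90 | 112 |

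The Control arm is short by 5 on the first basis and 6 on the second. The Test arm is not short on either. Setting 30 + 28 = 58 against 56 is not a fair comparison, because it adds subjects evaluated to subjects enrolled with a loss allowance. Since both tests take place at Visit 4, completers are the right basis.

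**Step 3: overlap that meets both sizes.** Overlap needed = 30 + 25 − Control completers.

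- 50 completers (full 10% loss): 55 − 50 = 5 shared subjects, or 5 / 25 = 20% of the contrast sensitivity group.
- 55 completers (one subject lost of 56): 55 − 55 = 0.

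In the first case 80% of the contrast sensitivity Controls still do only that test, which fits an expectation that participants will likely not do both.

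**Step 4: result if there is no overlap at all.** With contrast sensitivity filled first, 50 − 25 = 25 Controls remain for defocus curves, or 25 / 3 = 8.3 per pupil group if pupil sizes are evenly spread. For a given standard deviation, the standard error of a group mean grows by √(10 / 8.3) = 1.10, about 10%. Contrast sensitivity keeps its 25.

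**Step 5: what depends on these sizes.** Sections 5.1.1 and 5.1.2 make both outcomes descriptive, without hypotheses. Section 11.2.2 gives no power figure for either. The sample size statements in 11.2.1 concern the three primary acuity endpoints in the whole trial, and who sits in which sub-study does not alter them.

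**The case for a change.** The best case for a change has four parts.

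1. **The assumed 50 is favourable.** A subject without the assigned lens in the second eye has only monocular acuity measured (Sections 6.3.4 and 9.1.3), so cannot give a binocular defocus curve, and is also likely ineligible for contrast sensitivity. Each such Control completer leaves both pools and raises the overlap needed by one. This stands, but there is room: with full overlap the larger sub-study alone sets the demand, 30 of 50.
2. **The fallback is worded for scarce pupil sizes.** It does not say whether a subject already in the other sub-study counts as unavailable. That is a fair reading of the text. In practice the result is the same: the curve is drawn from however many were tested.
3. **No rule says which sub-study has first call on a subject.** This also stands, as a gap in operational detail. The public text does not show Appendix B, whose Section 9.0 holds the defocus methods, so it cannot be said that no such rule exists.
4. **The wording would be cheap to add.** It would, but a sentence permitting overlap permits what is not forbidden, and a target of about eight per group restates what the fallback already accepts.

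Uneven pupil sizes could leave one group well below eight. The documents give no pupil distribution, so the extent is unknown. This is the case for which the fallback was written, and it would arise with or without a second sub-study.

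**Conclusion.** No change follows. With no shared subjects and the full 10% loss, the Control arm is about five completers short of the two stated sizes together (55 against 50). That the two sizes cannot both be reached does not follow: about five Control subjects doing both tests would suffice, plus one for each Control completer without the assigned lens in the second eye, and nothing in the visible text bars them. If sites keep the groups fully apart, the shortfall can fall wholly on the Control defocus curves, at about eight per pupil group instead of ten. The plan accepts that number, and the loss of precision is small for a descriptive curve. Contrast sensitivity need not drop below its stated 25.

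This rests on the Synopsis figure of 50 Control completers, on an even spread of pupil sizes for the figure of eight, and on there being no separation rule in the part of Appendix B that is not public. Those running the sub-studies can manage the overlap as Visit 4 approaches, since Appendix A records photopic pupil size before surgery and again, in both eyes, at Visit 3B.

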#### 11.2.3 Overall Sample Size and Adjustment for Dropouts

To allow for losses of up to 10%, approximately [100/(1-0.1)] = 112 Test group subjects and approximately [50/(1-0.1)] = 56 Control group subjects will be enrolled. The overall enrollment target will be approximately 168 subjects.

